3.3. COMPLIANCE

Study compliance is one of the primary objectives to be measured as part of the feasibility trial. The study will quantify:

- 1. Self-reported treatment compliance: patient diaries will be completed with an option to complete usage time, in hours, of the treatment device. This diary will be returned for analysis at the two week follow up visit
- 2. Outcomes compliance: completion of outcome tools will be monitored with an expected completion of instrument items of 95%. Patients will be provided with a reminder to complete outcomes and provided with options for returning the 12 week follow up as electronic, postal or by telephone
- 3. Clinic attendance: clinic attendance will be monitored particularly the completion of 6 week follow up outcomes assessment.

3.4. PROGRESSION CRITERIA

The trial will progress to a full trial if all the following are fulfilled:

- 1. A suitable outcome measure can be determined using the feasibility data and the effect size of the three interventions estimated along with the standard deviations in order to properly power a definitive trial;
- 2. None of the interventions have an unacceptable complication rate as agreed by the trial steering committee;
- 3. Recruitment rates are greater than 50% anticipated allowing a full trial to be completed within a 3-year time frame within the U.K. Trauma Trials Network;
- 4. Study retention is greater than 60% at the 6-week follow up in all groups;
- 5. The effect size and standard deviation produces a sample size calculation that can be achieved across the trauma trials network within a reasonable time frame and within scope of an NIHR HTA funding;

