3. RESEARCH QUESTION AND AIMS

3.1. TRIAL PURPOSE

To establish the feasibility of performing a randomised trial to identify the best treatment for low-risk ankle fractures in school aged children

Objectives

Evaluation of the feasibility of a definitive randomised trial through:

- 1. Patient feasibility
 - a. Compliance with treatment and other outcome scores
 - b. Are there any complications with treatments?
- 2. Outcome feasibility
 - a. Determine the ideal outcome measure for this trial.
 - b. Determine the effect sizes of the interventions for a sample size calculation of a definitive trial
- 3. Site and clinician feasibility
 - a. Numbers of eligible patients
 - b. Recruitment and retention rates for this trial
 - c. Fidelity assessment of inclusion criteria and interventions

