3.2. OUTCOMES

Feasibility outcomes

Feasibility outcomes will determine if a future main trial is possible and desirable. The following feasibility outcomes will be assessed:

- Recruitment rates compared to site screening logs;
- Retention rates, drop out and crossovers;
- Adherence to treatments through a 14-day patient diary;
- Trial experience and qualitative feedback from participants.

Clinical outcomes

Clinical outcomes will be collected to assess the relevance and acceptability of these outcomes for use in a future definitive RCT and to validate the tools to measure outcomes for childhood fractures through:

- 1. Calculation of minimally important clinical difference for outcome tools;
- 2. Validation of PROMIS Mobility for ankle fractures in children.

The following clinical outcomes will be assessed:

- Physical function as measured by PROMIS Mobility;
- Quality of life as measured by EQ-5D-Y;
- Global rating of change score;

- Daily pain scores through a 14-day patient diary;
- Re-injury rates;
- Complications.

Safety endpoints

No significant safety issues are expected related to this trial. Spontaneous adverse events will be monitored during the trial, in particular at the 6-week follow up requiring additional treatment or physiotherapy.

Stopping rules and discontinuation

No specific stopping or discontinuation rules have been identified for this study. As this is a feasibility study, if the accumulating evidence shows that the study is not feasible then at the advice of the TSC, the sponsor reserves the right to stop the study at any time

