4.4. STATISTICS

Feasibility outcomes

All analyses will be documented in a Statistical Analysis Plan which will be finalised prior to database lock. Descriptive statistics (with 95% confidence intervals (CI) where appropriate) will address feasibility objectives (e.g. recruitment and follow-up rates, missing clinical outcome data, intervention adherence, standard deviations for clinical outcomes). Demographic and baseline clinical characteristics will be descriptively compared by study arm.

Assessment of efficacy

As this is a feasibility study, no formal assessment of efficacy will be undertaken. The potential primary clinical outcome for the future main trial will be analysed descriptively per arm, with confidence intervals generated using appropriate regression model to estimate the likely range of intervention effects. Secondary clinical outcomes will be descriptively summarised by treatment arm.

There is no consensus yet on the outcomes that should be measured in childhood fractures. In our preparatory work for this proposal families have identified 'return to normal activities' and 'pain' as the two most important outcomes.

Initial findings from the CORE-KIDS lower limb fracture study have suggested that the EQ-5D-Y and PROMIS Mobility outcome sets should be used as the primary outcome measures, as they assess a broad range of function and mobility domains.

A formal minimally important clinical difference (MCID) in this patient group has not been calculated, and previous trialists have used a range between 5 and 7%^{9,10} to represent an important difference.

Assessment of safety

No significant safety issues are expected related to this trial. Spontaneous adverse events will be monitored during the trial, in particular at the 6-week follow up requiring additional treatment or physiotherapy.

All adverse events will be discussed at the trial management group meetings. Significant adverse events will be escalated to the trial steering committee and study sponsor.

Procedures for missing, unused and spurious data

Proportions and patterns of missing data will be summarised by arm but there will be no imputation for missing data at follow-up assessments nor any model-based adjustment for missing data.

Baseline and outcome data will be summarised by allocated group, regardless of adherence with the intervention. Safety will be evaluated using the Safety set: All randomised participants who receive at least one treatment.

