6.2. SIZE OF SAMPLE

No formal sample size calculation is required for the feasibility trial. An estimate for the sample size of the full trial requires 969 patients for 90% power with a MCID for ASK-P of 5 and standard deviation of 16.5⁹. Assuming a 30% loss to follow up, for feasibility this requires 42 patients to be recruited into each group of the feasibility study.

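### Objective 2b and progression criteria 1 and 5 size the definitive trial, and decide whether it goes ahead, on an effect estimated from about 29 children per arm; the target difference should be an MCID

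*Protocol*

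**What the plan says.** Objective 2b (Protocol 3.1) is to "Determine the effect sizes of the interventions for a sample size calculation of a definitive trial". Section 3.4 opens with "The trial will progress to a full trial if all the following are fulfilled", so each criterion is binding. Criterion 1 needs a suitable outcome measure and "the effect size of the three interventions estimated along with the standard deviations in order to properly power a definitive trial". Criterion 5 needs this: "The effect size and standard deviation produces a sample size calculation that can be achieved across the trauma trials network", within a reasonable time and within funder scope.

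Other sections point a different way. Section 4.4 states: "As this is a feasibility study, no formal assessment of efficacy will be undertaken". It plans descriptive summaries by arm, with confidence intervals for the likely range of effects. Section 3.2 lists "Calculation of minimally important clinical difference for outcome tools" among the uses of the clinical outcomes. Section 6.2 gives a provisional full-trial size of 969 for 90% power, from an ASK-P MCID of 5 and an SD of 16.5, and then says: "Assuming a 30% loss to follow up, for feasibility this requires 42 patients to be recruited into each group of the feasibility study".

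**The concern.** A pilot of this size can estimate a standard deviation usefully. It cannot estimate a between-arm effect well enough to serve as the target difference of the next trial. The required sample size varies with the inverse square of the target difference, so sampling error in the estimate is magnified.

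Two errors follow. If the observed difference is large by chance, the definitive trial is too small to detect the difference that matters. If it is small by chance in absolute terms, the implied trial is very large, and criterion 5 could stop a trial worth doing. What is at stake is the go/no-go decision and the size of the definitive trial. The care of children in this study and the validity of its own data are not affected.

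**Working it through.** **Inputs.** From section 6.2: MCID 5, SD 16.5, power 90%, 42 per arm, 30% loss. From section 4.3: 1:1:1 allocation. From criterion 4: "Study retention is greater than 60% at the 6-week follow up in all groups". Assumed, because not stated: two-sided alpha 0.05, pairwise comparison, no multiplicity adjustment, no baseline adjustment.

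**The plan's own figure.** n per arm = 2 × (1.96 + 1.2816)² × (16.5/5)² = 228.9, so 229. Allowing for 30% loss, 229/0.7 = 327.1, so 328 per arm and 3 × 328 = 984 in total. The stated 969 is 323 per arm, or 323 × 0.7 = 226 evaluable, with power 89.6%. The figure is therefore reproduced to within 2%. It is MCID-based and appears to include the loss already.

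**Precision of the pilot effect.** Evaluable per arm: 42 × 0.7 = 29.4, taken as 29. The standard error (SE) of a pairwise difference is SD × √(2/n), and the half-width is t × SE, using the SD pooled over three arms (3n − 3 degrees of freedom).

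| Evaluable per arm | SE | 95% half-width, points | In SD units |
|---|---|---|---|
| 42 (no loss) | 3.60 | 7.1 | 0.43 |
| 29 (30% loss) | 4.33 | 8.6 | 0.52 |
| 25 (60% retention) | 4.67 | 9.3 | 0.56 |

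The target is 5 points, or 5/16.5 = 0.30 SD. At 29 per arm the half-width is 8.6/5 = 1.7 times the target.

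**Sample size implied by the estimate, if the true difference is 5.**

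- The quartiles of the observed difference are 5 ± 0.6745 × 4.33, that is 2.08 and 7.92.
- At 2.08, n = 2 × 10.507 × (16.5/2.08)², about 1,326 per arm (unrounded quartile used). At 7.92, n = 92 per arm. The MCID-based figure is 229.
- With 92 per arm, true power at a difference of 5 is Φ(5/(16.5 × √(2/92)) − 1.96) = Φ(0.095), about 54%.
- True power falls below 80% when the absolute observed difference exceeds 5 × 3.2415/2.8016 = 5.79. The probability is 0.428 + 0.006 = 0.43, the second term being the opposite direction.
- The implied size is more than double the MCID-based one when the absolute observed difference is below 5/√2 = 3.54. The probability is 0.34.

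**Sizing on the MCID and the pilot SD instead.** Pooled over 3 × 29 children there are 84 degrees of freedom. The chi-square 95% interval multiplies the SD by 0.87 to 1.18, so 16.5 becomes 14.3 to 19.4. With the target fixed at 5, that gives 173 to 318 per arm around 229. Even the lower end, 173, has true power of about 80% if the SD really is 16.5.

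**The case against.** The strongest defence is that effect size is undefined and may mean the MCID. The only worked calculation for the definitive trial uses an MCID, section 3.2 plans to derive one, and section 4.4 disclaims efficacy. This does show that the protocol follows the sound method elsewhere. It does not rescue the criteria. An effect size that belongs to the three interventions and is to be estimated is a between-arm quantity, whereas an MCID belongs to an instrument. The analysis plan may add detail, but it is the protocol that fixes the progression rule.

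Three further objections stand in part.

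- MCID 5 and SD 16.5 are ASK-P values, and this trial does not collect ASK-P. The figures carry over to PROMIS Mobility or EQ-5D-Y only if the MCID-to-SD ratio is near 0.30.
- Criterion 5 has no numerical limit, so the chance of failing it cannot be calculated. The 34% describes the implied size and is not a failure probability.
- Baseline adjustment would help. With an assumed correlation of 0.5 the half-width becomes 8.6 × √0.75, about 7.5, which still exceeds 5.

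Two stronger readings are tempting, and the document does not support them. A reader might infer that the primary outcome will be chosen by which measure shows the largest between-arm difference. Criterion 1 refers only to the feasibility data, and section 3.2 speaks of relevance, acceptability and validation. A reader might also infer that an estimate in the wrong direction would itself fail criterion 5. No arm is named as control, and the sample size depends on the squared difference, so only a small absolute difference matters.

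**Conclusion.** The concern holds. As written, objective 2b and criteria 1 and 5 use the estimated effect both to size the definitive trial and to decide whether it proceeds, contrary to the approach in sections 3.2, 4.4 and 6.2. Under the stated assumptions (ratio 0.30, two-sided 0.05, 29 per arm, true difference equal to the MCID), the middle half of pilots, ranked by observed difference, would imply 1,326 down to 92 evaluable children per arm instead of 229. The fault is confined to the effect size, since the pooled SD from this trial is usable.

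This should be fixed, but it is not critical to the present study: nothing in its conduct or data collection depends on it, and the remedy is wording.

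**What to change.** Remove effect size from objective 2b and from criteria 1 and 5. State instead that the definitive sample size will use:

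- a target difference equal to a justified MCID for the chosen outcome, either pre-stated or informed by the MCID work in section 3.2; and
- the pooled within-arm SD from this trial, preferably with an allowance for its uncertainty.

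Criterion 5 then asks whether the size from those two inputs is achievable. Between-arm estimates and confidence intervals stay descriptive, as section 4.4 already provides.

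The cost is a protocol wording change, with no extra children or data. An allowance for SD uncertainty makes the next trial somewhat larger. As one optional convention, the one-sided 80% upper limit multiplies the SD by 1.07 and the sample size by 1.07², about 1.15. An MCID derived from this trial would itself be imprecise, so its justification should not rest on these data alone.

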4. STUDY DESIGN AND METHODS OF DATA COLLECTION AND DATA ANALYSIS

4.1. TRIAL CONFIGURATION

A prospective three-arm, parallel, multicentre, feasibility randomised trial with an embedded interview study exploring attitudes and experience of participating in a trial

4.2. DETAILS OF PRODUCT(S)

The ANCHOR Trial is a randomised, feasibility trial. This design will permit evaluation of trial feasibility and deliver validation data for outcome instruments used in childhood lower limb fractures.

Products will be prescribed for the ANCHOR Trial population. Participants will be randomised to receive a supportive bandage, removable brace or walking cast.

Product Description

- 1. Supportive bandage. An elastic bandage (e.g. tubigrip) will be provided for the child to wear for two weeks. The bandage will be sized according to manufacturer instructions.
- 2. Semi-rigid, removable brace (including splints or custom orthoses). A removable ankle brace (e.g. Aircast Air-Stirrup Ankle Brace, removable weightbearing backslab Walker boot or Aircast boot) will be prescribed at the discretion of the local treating physician. The device will be sized and fitted according to manufacturer instructions.
- 3. Below knee walking cast. A non-removable, below knee walking cast will be applied according to local protocols. The cast may be synthetic or resin based and will be applied over standard padding. The cast will be circumferential or a backslab but must be constructed to bear weight and will be applied and removed by a trained member of staff.

Manufacture

Local NHS supply chain approved devices will be prescribed in each centre and used according to manufacturer guidelines.

Known Side Effects

Previously reported side effects of treatments include:

Pressure related injuries e.g. marks and blisters – This is more common in the removable brace group than cast group and is associated with patients not wearing the supplied protective sock [22]. This will be mitigated by reminding this group to wear the sock and by ensuring patients in brace or cast have adequate padding.

Plaster saw injuries – removal of a below knee walking cast requires the use of an electronic oscillating plaster saw which may cause injury. Injury is typically caused through thermal damage to the skin. This will be reduced by requiring casts to be applied and removed by trained and experienced personnel. This is in line with the 2015 British Orthopaedic Association Casting Standards (https://www.boa.ac.uk/uploads/assets/uploaded/83dcfe25-307e-4e82-abf362976f08a3ae.pdf)

4.3. RANDOMIZATION AND BLINDING

Participants will be individually allocated in a 1:1:1 ratio to one of the three treatment groups using a minimisation algorithm by the Nottingham Clinical Database Support Service (CDSS) and held on a secure server. The minimisation variables will comprise age, injury type and study site. The investigator or authorised designee will use the remote, internet-based randomisation system to obtain the treatment allocation for each participant. Other than the allocated treatment, all groups will be followed up in the same way to exclude bias.

It will not be possible to blind participants to treatment allocation. Assessor blinding will be achieved by removal of the treatment device by nursing staff independent to the trial on arrival to follow up clinic for those children who require an appointment to remove a cast. Follow up will be performed remotely by the central trial team. Non-response will be minimised through the use of electronic and telephone reminders.

Maintenance of randomisation codes and procedures for breaking code

Access to the randomisation system will be confined to the CDSS IT staff.

In most cases, the un-blinding will be part of managing an SAE, and will be reported with the SAE, however, in cases where un-blinding was not associated with an SAE, such actions should be reported in a timely manner. The default will be to use the same timeline requirements for investigator reporting of SAEs (notification of Sponsor immediately as practicable by phone or email, followed by a written narrative of the event within 48 hours).

No interim analysis is planned during this study. At the end of the study, anonymous linked records of outcomes and treatment allocation will be provided for analysis.

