5.1. STUDY ACTIVITIES FOR THE TRIAL

At time of diagnosis (typically in the Emergency Department), potential participants may be identified and provided with a patient information sheet by the usual care team. Screening of participants may also be performed by the usual care team in face-to-face or virtual fracture clinics and information sheets provided.

CONFIDENTIAL ANCHOR Trial Protocol v3.2 28.02.22 IRAS ID 277534 page 19 of 33
FUNDED BY
NIHR National Institute
for Health Research

Where eligible participants wish to join the study, a member of the research team will obtain informed consent and undertake randomisation to a product at the point in the local care pathway where a definitive treatment is being offered. This may be in the Emergency Department, Emergency clinics or fracture clinic depending on the local pathways.

Following completion of pre-injury baseline scores and CRF, the patient will be randomised using a web-based electronic randomisation with 1:1:1 allocation with stratification for fracture type (occult and visible fracture line) and child age (5-10, 11-15) with block sizes of 3, 6 & 9.

Treatment will be provided according to random allocation by a trained member of the clinic staff according to the manufacturer's guidelines. As described in section 4.2, the available treatments are:

- 1. Supportive bandage.
- 2. Semi-rigid, removable brace (including splints or custom orthoses).
- 3. Below knee walking cast

Routine follow up will be provided according to local protocols and decided by the usual care team. Patients who have a below knee walking cast are likely to require a clinic review to remove the device. Other patients may be discharged with instructions to remove their own device at home.

A patient diary is provided to participants at time treatment is provided. The diary is returned after two weeks.

Outcome assessment will be completed by the central research team using an electronic interface through the Redcap system. Outcomes will be collected at 2 weeks, 6 weeks and 12 weeks. Telephone, SMS text messages (Esendex, Nottingham) and e-mail reminders will be used to encourage completion of outcome scores.

	Baseline (pre- injury) score	Review 1 (Day 7-23)	Review 2 (Day 35-52)	Review 3 (Day 84-100)
Demographics	Х			
Physical function (PROMIS Mobility)	х	х	Х	Х
Quality of life (EQ-5D-Y)	х	Х	х	Х
Daily pain (faces pain or VAS)	х	Х		
Re-injuries			Х	Х
Complications		Х	Х	Х
Parent satisfaction			Х	Х
Child satisfaction			Х	Х

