6. SAMPLE AND RECRUITMENT

6.1. ELIGIBILITY CRITERIA

Inclusion criteria

Children (aged 5-15 years inclusive) will be suitable for inclusion in the study if they have:

- A proven low-risk ankle fracture on x-ray
 - o minimally displaced or undisplaced fibular fracture
- A clinical undisplaced fracture which fulfils the Ottawa criteria:
 - o A history of trauma
 - o Tenderness at the posterior edge of the lateral malleolus
 - Unable to weight bear for more than 4 steps
 - o No alternative cause of pain identified on x-ray

Exclusion criteria

Children will be excluded if

- The injury is more than 7 days old at randomisation
- They in conjunction with their parents are unable to complete the outcome measures chosen in English.

• The child is on the Child Protection Register or where there is any concern about the cause of the injury.

Expected duration of participant participation

Study participants will be participating in the study for 12 weeks

Removal of participants from therapy or assessments/Participant Withdrawal

Participants may be withdrawn from the trial either at their own request or at the discretion of the Investigator. The participants will be made aware that this will not affect their future care. Participants will be made aware (via the information sheet and consent form) that should they withdraw the data collected to date cannot be erased and may still be used in the final analysis. Enrolled participants in the ANCHOR TRIAL who are not yet randomised can be replaced (though keeping their trial ID), but participants who withdraw after randomisation will not be replaced.

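### Section 5.1 discloses the block sizes, including blocks of 3, to recruiters in an open three-arm trial, and Section 4.3 does not say whether its minimisation has a random element

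*Protocol*

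**What the plan says.** The protocol describes allocation in two places.

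- Section 4.3: "Participants will be individually allocated in a 1:1:1 ratio to one of the three treatment groups using a minimisation algorithm". It continues: "The minimisation variables will comprise age, injury type and study site". Nothing is said about a random element, either way.
- Section 5.1: web-based 1:1:1 randomisation "with stratification for fracture type (occult and visible fracture line) and child age (5-10, 11-15) with block sizes of 3, 6 & 9". Site is not a stratum.

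These are different methods and have to be reconciled in any case. The present point is what each one lets a recruiter predict.

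The setting is open: "It will not be possible to blind participants to treatment allocation". Allocation is central: "The investigator or authorised designee will use the remote, internet-based randomisation system to obtain the treatment allocation for each participant". On the list itself, Section 4.3 says: "Access to the randomisation system will be confined to the CDSS IT staff". Section 5.1 places randomisation after consent, baseline scores and the case report form.

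Section 4.4 plans no formal efficacy assessment, but it does plan model-based confidence intervals for the likely intervention effects. Section 3.1 (objective 2b) and Section 3.4 (criteria 1, 2 and 5) carry effect sizes, standard deviations and complication rates into the decision on a definitive trial.

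**The concern.** Central allocation hides the next assignment, but it does not stop anyone predicting it from past assignments that are open to view. Two things make prediction easier: knowing the block sizes, and balancing within a unit whose whole history the recruiter can see, such as the site.

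A recruiter who can guess the next device can time or steer enrolment before randomisation. A possible motive is on record: Table 2 reports a workshop view that some families regard the elasticated bandage as less protective. If children with worse symptoms were steered away from one arm, that arm's outcomes and complications would look better than they are. Balancing on injury type would not remove selection on severity within a type.

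The effect estimates, standard deviations and per-arm complication rates feed the progression decision, so concealment deserves protection here even without an efficacy test.

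**Working it through.** The protocol gives no predictability figure, so there is none to reproduce.

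**Inputs from the protocol.** Three arms at 1:1:1; 42 per group, so 3 × 42 = 126 children (Section 6.2); two fracture types × two age bands = 4 strata, with blocks of 3, 6 and 9 (Section 5.1); minimisation on age, injury type and site (Section 4.3).

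**Assumptions.** Equal-sized sites, 1 to 10 in number; 50:50 factor levels; equal factor weights; block sizes drawn at random.

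**Step 1: allocations fixed in advance when block boundaries are known.** In a block of 3k children with k per arm, the determined allocations are the final run of a single arm. Its expected length is the sum over j of P(last j all in the same arm).

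- k = 1: 1, so 1/3 = 33%.
- k = 2: 1 + 3 × (2 × 1)/(6 × 5) = 1.2, so 1.2/6 = 20%.
- k = 3: 1 + 3 × (3 × 2)/(9 × 8) + 3 × (3 × 2 × 1)/(9 × 8 × 7) = 1.286, so 1.286/9 = 14%.

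With the three sizes equally frequent, the overall share is (1 + 1.2 + 1.286)/18 = 19%. With 6 and 9 only, it is (1.2 + 1.286)/15 = 17%. These are upper limits, because they require the recruiter to know where each block starts and how long it is.

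**Step 2: what a recruiter at one site sees.** The average block has (3 + 6 + 9)/3 = 6 allocations and is shared across sites. At five equal sites, one site sees about 6/5 = 1.2 of them; at two sites, 3.

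**Step 3: correct-guess rates by simulation** of 126 children (chance 33.3%). There were two independent sets: 1,500 minimisation trials per setting for 2, 3, 5, 8 and 10 sites, with block runs at 1, 2, 3 and 5 sites; and 400 trials per setting for 1, 3, 6 and 10 sites. The recruiter guesses the arm used least so far: in the child's stratum for blocks, at the site for minimisation. Where both sets cover a cell, both results are shown.

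| Own-site knowledge only | 2 sites | 3 | 5 | 6 | 10 |
|---|---|---|---|---|---|
| Blocks as in 5.1 | 39.0% | 37.1%, 37.5% | 35.8% | 35.7% | 35.1% |
| Minimisation, if deterministic | 57.8% | 56.1%, 56.5% | 54.2% | 54.7% | 52.1%, 53.0% |
| Minimisation, best arm with probability 0.8 | 51.5% | 49.9%, 50.5% | 48.0% | 48.5% | 46.5%, 46.6% |

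The 5- and 6-site columns come from different sets with slightly different imbalance scores, so the small reversal between them means nothing.

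For a recruiter who knows every site's history, or when there is only one site, blocks give 54-55%. With all-site history, deterministic minimisation gives about 82%, and about 70% with the 0.8 probability.

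**Step 4: gain from a random element.** At 2 sites: 57.8 − 51.5 = 6.3 points, out of an excess over chance of 57.8 − 33.3 = 24.5. At 10 sites: 52.1 − 46.5 = 5.6 out of 18.8. So between a quarter and a third of the excess goes.

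**The case against.** Several stronger readings are tempting, and the protocol does not support them.

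- **The minimisation is deterministic.** A reader might infer this from the silence in Section 4.3. The section neither states nor excludes a random element, and a restricted specification may well contain one. The 52-58% range is therefore conditional.
- **Allocation can be guessed locally whichever method is kept.** This fails for the blocks as written. They run across sites and vary in size, so own-site guessing stays near chance. The 54% figure needs one dominant site or shared allocations, whereas Section 5 describes a multicentre trial.
- **Unwanted children can be dropped without trace.** Section 6.1 does say "Enrolled participants in the ANCHOR TRIAL who are not yet randomised can be replaced", but it adds that they keep their trial ID. Section 7.9 requires a recruitment log of everyone enrolled, and Section 3.2 compares recruitment with screening logs. A child dropped at that stage remains visible.
- **The comparison will be biased.** The simulations give guess rates only. No bias in effect size, standard deviation, complication rate or recruitment has been quantified; no formal efficacy test is planned; and the protocol gives no sign that recruiters would select. The view in Table 2 is attributed to families.

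It is also fair to say that a random element helps only modestly while site remains a factor.

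What survives is narrower. The block sizes are printed in the protocol that sites work from, publishing them serves no purpose there, and one of them equals the number of arms.

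**Conclusion.** The point holds in a limited form. Disclosing block sizes of 3, 6 and 9 in an open three-arm trial is an avoidable weakness in concealment. Its practical size is small with several similar sites (about 35-39% correct against 33%) and material if one site dominates or allocations are shared (about 54%). Since the number of sites and their shares are not stated, the protocol does not show which case applies.

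For minimisation, the finding is only that Section 4.3 should settle whether there is a random element. Without one, own-site guessing would be about 52-58% correct at 2 to 10 equal sites; with a 0.8 probability, about 47-52%. That removes certainty but not predictability.

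Any resulting bias would touch descriptive estimates and complication rates used for progression, and its size is unknown. All rates rest on the assumed equal sites, even factor levels and equal weights.

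**What to change.** Settle on one allocation method, then make the matching change.

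- **If blocks are kept:** in Section 5.1, replace the block-size clause with a statement that block sizes vary at random and are not disclosed to sites. Drop blocks of 3 and hold the sizes in a restricted CDSS specification.
- **If minimisation is kept:** confirm in Section 4.3 that the algorithm includes a random element, with the probability held by CDSS only. If the system has none, add one.

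The cost is a wording amendment and at most a system setting, with no extra children or staff. The downside for blocks is slightly looser balance within strata. Within a block of 3k the largest difference between two arms is k, that is 1, 2 or 3 for the three sizes. Blocks of 9 are already allowed, so the worst case per stratum stays at 3. For minimisation, balance on the three factors loosens slightly if a random element has to be added.
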